### **Product Description:**

The SCIO device is an FDA-Approved Class Type IIa medical device which calibrates voltage and amperage to adjust to the body's stress levels in real time whilst administering PEMF therapy. It controls the levels of electricity that are conducted into the body through the head, wrist, and ankle harnesses. The device runs through a DC electric current, with a maximum voltage of 5 volts.

The SCIO device offers a calibration of the body. It emits a low voltage, direct current that is safe for humans. It works through an Artificial Intelligence system which is controlled through a software on a computer or laptop and connected through a USB to the Scientific Consciousness Interface Operations device.

### **Product Intended Use:**

To emit PEMFs into the body and observe effects on treating PTSD and Trauma.

### **Potential Benefits and Risks to Patients**

Every effort is taken to ensure that screening and production of the clinical trial follows a code of ethics. Patients are not at risk of contracting harmful diseases, ailments, or any other negative symptoms. The trial is held in a COVID-19 safe environment, with regular cleaning, monitoring, and health checks performed regularly by staff.

Patient and staff safety is a priority of the clinical trial. To ensure this, potential patients were screened and interviewed in advance of the trial to ensure that they fit the correct profile for the study. They were asked about their medical history, and the accessibility of the clinical trial location in relation to their home. The clinical trial timeframe was agreed upon with all patients to ensure they arrived at their session at the correct time. Patients had the option to drop out of the clinical trial at any point.

There have been no recorded negative side effects to Pulsed Electromagnetic Therapy in the treatment of patients. In the clinical experience of the Investigator, approximately 1% of patients have reported experiencing headaches or dizziness during and/or immediately after a session using the SCIO device. This side effect was not reported to be severe and did not last longer than 12 hours.

Therefore, it is prudent to assume that there will not be any negative health side effects from this clinical trial. Patients were made aware of this potential side effect prior to the trial.

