### **Expected Outcomes:**

It is expected that all patients will see an improvement in their symptoms relating to PTSD and Trauma. Previous studies into the benefits of PEMF therapy have indicated a significant improvement in both physical and mental health conditions. Whilst we do not expect a complete recovery, we expect to see a marginal improvement from all patients. There is no expectation of any adverse outcomes or reactions to the PEMF therapy, apart from headaches or dizziness. All patients have access to [name] during the clinical trial.

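### The risk section denies any recorded side effect, reports one in about 1% of patients on the trial device, and still concludes that none need be expected

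*Combined protocol and SAP*

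**What the plan says.** All of this comes from the combined protocol and SAP.

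Potential Benefits and Risks to Patients makes these statements, in this order:

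- A general assurance: "Patients are not at risk of contracting harmful diseases, ailments, or any other negative symptoms". A sentence on COVID-19 precautions follows it.
- A denial: "There have been no recorded negative side effects to Pulsed Electromagnetic Therapy in the treatment of patients".
- A report, attributed to the investigator's clinical experience: "approximately 1% of patients have reported experiencing headaches or dizziness during and/or immediately after a session using the SCIO device".
- A description of that report: "This side effect was not reported to be severe and did not last longer than 12 hours".
- An inference: "Therefore, it is prudent to assume that there will not be any negative health side effects from this clinical trial".
- A disclosure: "Patients were made aware of this potential side effect prior to the trial".

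Expected Outcomes says: "There is no expectation of any adverse outcomes or reactions to the PEMF therapy, apart from headaches or dizziness".

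The results section During The Trial says that all patients kept their appointments and that none reported a negative side effect. Reflections and Considerations later says that two sessions a week tired patients, and it raises the possibility of exhausting them.

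**The concern.** A reader of the risk section is told that nothing has been recorded, that something has been recorded, that nothing need be assumed, and that patients were warned of it. These statements cannot all stand. The inference is the most serious of them, because it turns a small but non-zero rate on the trial device into an assumption of no harm.

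What is at stake is the safety message, not any efficacy figure. The document closes by recommending larger trials and by presenting PEMF as an alternative to prescription medication. If the no-harm wording is carried into that work, next to a trial in which no side effect was reported, a reader may take the one as evidence for the other. Five patients cannot supply that evidence.

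**Working it through.** **Step 1. Do the statements concern the same treatment?** Product Description says that the SCIO device "calibrates voltage and amperage to adjust to the body's stress levels in real time whilst administering PEMF therapy". SCIO sessions are therefore PEMF therapy, and the device behind the 1% is the one used in this trial. A side effect reported with SCIO falls within the scope of the denial.

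**Step 2. The statements side by side.**

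| Statement | Implied position |
|---|---|
| Denial (risk section) | Nothing on record |
| Report (risk section) | Headaches or dizziness in about 1% |
| Description (risk section) | The text itself calls this a side effect |
| Inference (risk section) | None to be assumed |
| Disclosure (risk section) | A potential side effect exists |
| Expected Outcomes | None expected, except headaches or dizziness |

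The report and its description contradict the denial. The inference does not follow from a rate above zero. Expected Outcomes also contradicts the inference, because it carries the exception that the risk section drops.

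**Step 3. Can the 1% be reproduced?** No. Neither a numerator nor a denominator is given. It is used below as stated, with an assumed range of 0.5% to 2% to show how much depends on it.

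**Step 4. What would five patients show at that rate?** Inputs: n = 5 patients and 6 sessions each (Study Design), so 5 × 6 = 30 sessions; p = 0.01 (risk section).

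- Chance of no case, per patient: (1 − p)^n = 0.99^5 = 0.951.
- Chance of at least one case: 1 − 0.951 = 0.049. For p = 0.005 it is 0.025, and for p = 0.02 it is 0.096.
- The document gives the 1% per patient. If it were instead a rate per session, with independent sessions (an assumption), the chance of at least one case would be 1 − 0.99^30 = 0.260. For 0.5% and 2% it would be 0.140 and 0.455.

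On the stated per-patient reading, no cases is the expected result even if the 1% is exactly right.

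**Step 5. What does none in five exclude?** Input: 0 of 5 patients (During The Trial). The exact one-sided 95% upper limit solves (1 − p)^5 = 0.05:

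- p = 1 − 0.05^(1/5) = 0.451.
- The upper end of a two-sided 95% interval is 1 − 0.025^(1/5) = 0.522.

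The result is compatible with the quoted 1% and with rates far above it. It neither checks the 1% nor supports an assumption of none.

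**Step 6. Is the zero itself secure?** During The Trial reports no negative side effects. Reflections and Considerations says that the session frequency tired patients. Whether tiredness was considered a side effect, and in how many patients, is not stated. The limit in Step 5 applies only if the count of zero stands.

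**The case against.** The strongest defence is that the denial refers to PEMF therapy in general and the 1% to one investigator's use of one device. The text does not draw that distinction, and Product Description describes SCIO as delivering PEMF. Even if the distinction is granted, the inference about this trial still fails, because this trial used SCIO.

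Several other points against the concern do stand.

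- **Disclosure.** The section gives the effect, its approximate rate, its severity and its duration, and says that patients were told. A reader might infer concealment or serious harm. The document supports neither.
- **Origin of the 1%.** A reader might infer that the figure is recalled from memory or was gathered unsystematically. The text says only that it reflects the investigator's clinical experience, and clinic records are equally possible. The fair request is for its source and counts.
- **The general assurance.** Its wording suggests illness caught at the site, and COVID-19 measures follow directly. It is loosely worded and a weaker limb, not a clear second contradiction.
- **Reach of the section.** A reader might take it as the sole safety basis of the trial. Product Description separately calls the current safe, the withdrawal section provides for stopping the trial for unacceptable risk, and the claimed ethics exemption rests on other grounds.
- **The binomial figures.** The contradiction is textual and needs no arithmetic. The figures matter only for what the trial's zero can be said to show.

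**Conclusion.** Wrong as written. The risk section contradicts itself in adjacent sentences, and its no-harm inference is unsupported and conflicts with Expected Outcomes. This can be established from the text alone.

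The size concerns what may be said about safety. None in five has probability 0.951 at the stated 1%, and it leaves per-patient rates up to about 45% compatible (one-sided 95%). Those figures assume independent patients with a common rate, that any effect would have been reported and counted, and that the zero stands despite the remark about tiredness. The 0.951 also takes the unsourced 1% at face value.

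A reader might infer from the 45% that the true risk is high. It is a limit set by five patients, not an estimate. A reader might also infer that the trial's conclusions on symptoms are affected; no efficacy figure changes.

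**What to change.** In Potential Benefits and Risks to Patients:

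1. Delete the sentence "There have been no recorded negative side effects to Pulsed Electromagnetic Therapy in the treatment of patients" and the sentence "Therefore, it is prudent to assume that there will not be any negative health side effects from this clinical trial".
2. Qualify the general assurance so that it plainly does not cover effects of the device.
3. Keep the reported effect as it stands: about 1% in the investigator's clinical experience, not severe, no longer than 12 hours. Add its source, numerator and denominator, or say that these are not available. State whether the rate is per patient, as written, or per session.
4. Align the expectation with the exception in Expected Outcomes, so that both sections say the same thing.

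In During The Trial:

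5. Add that the absence of reports among five patients cannot exclude side effects, with the one-sided 95% upper limit of about 45% for 0 of 5.
6. Reconcile the report of no side effects with the remark in Reflections and Considerations that the sessions tired patients. Say whether tiredness was counted and, if so, in how many patients, and recompute the limit if the count changes.

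The cost is rewording, a look-up of the source of the 1%, and a slightly less favourable safety statement. No efficacy analysis changes.

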## **Methods:**

### **Study Design:**

Single-arm study involving five (5) subjects undergoing 6 90-minute sessions of Pulsed Electromagnetic Therapy. All patients received the same treatment. Harnesses were placed on the head, wrists, and ankles of the body to conduct the electromagnetic frequencies. Patients were encouraged to rest and relax whilst the therapy was conducted, as it does not require any tasks by the patient. Patients were required to complete a questionnaire before and after the trial. This questionnaire enquired about the different symptoms related to PTSD and Trauma, and asked patients to rate their symptoms on a scale. These questionnaires would form the foundation of the study's findings, as it would give a clear comparison of symptoms before and after the trial.

All aspects of the trial were exempt from a U.K. ethics committee board review because the trial was a non-invasive method of treatment, did not collect and tissue or fluid samples and the device is CE-marked and had been used in other trials previously approved and published on Clinical Trials.gov. Documents were provided on clinicaltrials.gov as evidence of this exemption.

All patients were from the inclusion criteria, and any patients exhibiting cases from our exclusion list were rejected from the pilot study. Patients were recruited through the National Centre for Electromagnetic Therapy social media pages, including Facebook, Instagram, and [www.ncet.co.uk](http://www.ncet.co.uk).

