**Background:**

PTSD and Trauma is often developed after a traumatic experience. These experiences can range from sexual assault, war, health problems, childbirth, or road accidents. PTSD and Trauma is estimated to [affect 3% of the U.K. adult population](#), with a tendency for women to have more of a lifetime prevalence (10-11%) as compared to men (5%). It is unclear why some individuals develop PTSD after traumatic events compared to those who do not.

Treatment for PTSD and Trauma available through the [NHS](#) include Cognitive Behavioural Therapy (CBT) or medication, including citalopram, paroxetine, sertraline, or phenelzine.

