### **Clinical Trial Outline**

**Prior to Trial** – Selected patients are required to fill out questionnaire provided to them by NCET.

**Week 1** – All patients receive two hours' worth of PEMF treatment across two separate sessions.

**Week 2** – All patients receive two hours' worth of PEMF treatment across two separate sessions.

**Week 3** – All patients receive two hours' worth of PEMF treatment across two separate sessions.

**Week 4** – All patients are required to fill out questionnaire provided to them by NCET. Dissemination of study and findings published.

Whilst the clinical trial is short in length, the ability for patients to get in contact with NCET is always available. Contact can be maintained between the patient and company regarding their lives after the trial. Information provided by patients after the trial has finished will be considered in the trials' findings.

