### **During The Trial**

There were no changes to the initial plan for the clinical trial. All patients attended their arranged appointments and reported no negative side effects to the treatment.

The Lead Practitioner noted valuable verbal feedback during sessions with each patient.

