## **Reflections and Considerations**

The clinical trial highlights the many benefits of PEMF therapy in treating symptoms related to PTSD and Trauma. All patients felt a significant improvement in their lives and indicated a wish to continue with PEMF therapy after the clinical trial had concluded. It can also be suggested that taking the time out of a daily schedule to attend PEMF therapy allows a patient to relax and rest. This form of meditation can be hypothesised as a beneficial side effect to PEMF therapy.

It should also be noted that patients with previous experience with Cognitive Behavioural Therapy (CBT) were more receptive to treatment, especially within the first two sessions. This is due to the selected patients (two of the five patients in the study) being able to communicate their triggers and emotions more clearly to the Lead Practitioner during PEMF treatment. This allowed the patients to experience a form of CBT with the clinical trial staff, whilst providing them time to relax out of their regular schedule. These two patients especially saw an improvement with sleeping, indicating that the opportunity to vocalise their symptoms and emotions helped them alleviate PTSD-related problems.

Whilst the clinical trial was a success in achieving the primary objective, there are numerous considerations and reflections for further clinical trials into PEMF therapy.

- A larger study would be beneficial in further analysing the benefits of PEMF therapy in treating PTSD and Trauma. Access to a larger cohort of volunteers, with a larger time frame of more PEMF sessions would produce a larger result pool. This would also allow for a control group, a treatment group, and a sham group to compare results more accurately and draw wider conclusions to the specific benefits of PEMF treatment.
- Twice weekly sessions proved to be tiring for patients (see Patient Three's statement above), therefore a longer, more spaced-out study would allow patients to recover from PEMF treatment before their subsequent sessions. This would remove the risk of exhausting the patients which may hamper accurate results of the study.
- This study was restricted due to financial and time restraints. Staff numbers were restricted to the Lead Practitioner and a Research Assistant to disseminate results. The financial impact of conducting a clinical trial for free dictated that the trial would be short to make it viable for the sponsor's funding.

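### The conclusion credits PEMF with the improvement and leaves out the in-session conversation that the report itself says helped patients

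*Combined protocol and SAP*

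**What the plan says.** **Treatment as described.** Study Design says "All patients received the same treatment", places harnesses on the head, wrists and ankles, and adds "Patients were encouraged to rest and relax whilst the therapy was conducted, as it does not require any tasks by the patient". The Clinical Trial Outline lists questionnaires and, for each of the three weeks, "All patients receive two hours' worth of PEMF treatment across two separate sessions". Neither section mentions conversation with staff.

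**Treatment as reported.** During The Trial records: "The Lead Practitioner noted valuable verbal feedback during sessions with each patient". Reflections and Considerations says that the two patients with earlier CBT experience were more receptive, and explains this by their "being able to communicate their triggers and emotions more clearly to the Lead Practitioner during PEMF treatment". It continues: "This allowed the patients to experience a form of CBT with the clinical trial staff". It then notes that sleep improved especially in these two, "indicating that the opportunity to vocalise their symptoms and emotions helped them alleviate PTSD-related problems". The Background says that NHS treatments for PTSD "include Cognitive Behavioural Therapy (CBT) or medication, including citalopram, paroxetine, sertraline, or phenelzine".

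**Attribution.** The Discussion says that physical symptoms improved with PEMF. The closing conclusion, in the last paragraphs before the Endnotes, declares the primary objective met by means of PEMF. It also presents PEMF as a beneficial alternative to prescription medication.

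**The concern.** The authors name a contributor other than the device and make a causal statement about it: talking about symptoms helped. In the report's own terms it is also a form of a treatment listed in the Background for the condition under study. The conclusion then assigns the result to PEMF without mentioning it.

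The conclusion is what most readers will take away, and it is used to recommend larger trials. A reader who stops there would think that the device was the only candidate explanation the authors had identified. A reader of Study Design would not learn that sessions included conversation.

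**Working it through.** This is mainly a comparison of sections. The arithmetic only shows what the reported means can and cannot tell us.

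**Step 1: sections side by side.**

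| Section | Content of sessions | What is credited |
|---|---|---|
| Study Design; Clinical Trial Outline | Device and rest; device sessions only | – |
| During The Trial | Verbal feedback with each patient | – |
| Discussion | Relaxing therapy | PEMF for headaches, fatigue and flashbacks; rest and relaxation as a hypothesis linked to insomnia and anger |
| Reflections and Considerations | Conversation with staff, a form of CBT for two of five | Talking, especially for sleep; time out to relax |
| Closing conclusion | – | PEMF |

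Conversation is credited in Reflections and absent from the conclusion. No later sentence withdraws it.

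**Step 2: reproduce the reported change.** Sleep is the domain that Reflections links to talking, and the closest rated item is difficulty falling asleep. Its mean is 5.6 before (Prior to the Trial) and 8.2 after (After The Trial). 8.2 − 5.6 = 2.6, as reported.

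**Step 3: can the means locate this gain?** The report calls its averages weighted but gives no weights, so I take simple means of five ratings. The totals are 5 × 5.6 = 28 before and 5 × 8.2 = 41 after, a gain of 13 points. Let g be the combined gain of the two patients described as having a form of CBT. The other three then have a mean gain of (13 − g)/3, and the two account for g/13 of the total. I assume a 1 to 10 scale and no net worsening in either group. The conclusion itself says that no worsening was recorded.

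| g | Mean gain, the two | Mean gain, other three | Share from the two |
|---|---|---|---|
| 0 | 0.0 | 4.33 | 0% |
| 6 | 3.0 | 2.33 | 46% |
| 8 | 4.0 | 1.67 | 62% |
| 10 | 5.0 | 1.00 | 77% |
| 13 | 6.5 | 0.00 | 100% |

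Every row fits the reported means.

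**Step 4: what this does not show.** The share coming from two patients is not the share caused by conversation. Those two also had the device and the rest, and the other three also gave verbal feedback. Even a listing of individual ratings would leave the causes mixed, because no patient had one component without the others.

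**The case against.** **The Study Design sentence is true as written.** In a single-arm study, beside the session count and harness placement, it most naturally means one device regimen for all. A reader might infer that it is contradicted, or that two patients were given a different treatment. The documents do not support that. Verbal feedback is recorded with each patient, and the two are said to have communicated more clearly, which describes the patients and not something extra delivered by staff. This part of the objection stands. What remains is that the description is incomplete.

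**A form of CBT is a loose remark.** No CBT protocol or qualified provider is described, so one cannot infer that CBT as such was delivered. That is right. The point needs only the authors' own statement that talking helped.

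**The report discloses all this and offers other explanations.** The Discussion suggests rest and relaxation in connection with insomnia and anger, and its sentence on physical symptoms does not concern sleep. Reflections adds time out of the daily schedule. It also proposes control and sham groups soon after describing the conversation, so a planner reading that proposal would have the disclosure at hand. This weakens the case against the Discussion. It does not repair the conclusion, which drops the caveats.

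**Without a control, nothing can be attributed anyway.** True, and conversation is one named part of that wider limit. But the conclusion makes the attribution despite it.

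**Conclusion.** The point holds as an inconsistency of attribution. The closing conclusion, and less clearly the Discussion, credits PEMF and omits a contributor that the authors say helped two of the five patients. The design cannot separate device, conversation and rest.

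The size is qualitative: it changes what the trial may be said to have shown, and no reported figure is wrong. The 2.6-point sleep gain does not measure the problem. It is a five-patient mean, Reflections speaks of sleeping without naming that item, and the range from none to all of the 13 points rests on the assumptions stated with the calculation. A reader might infer that conversation explains the sleep result. The documents support that no more than they support the device explaining it.

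One limit: the individual patient statements to which the Discussion and Reflections refer were not in the text available to me. They may describe the conversations further, but they would not alter the wording of the conclusion.

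**What to change.** In the Discussion and the closing conclusion, replace the attribution to PEMF with: *The changes followed PEMF sessions that included rest and conversation with staff and cannot be attributed to the device.*

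In Study Design, clarify the sentence on treatment: *All patients had the same schedule of device sessions and also talked with staff during sessions.* A cross-reference to Reflections and Considerations can cover the two patients for whom this is described as a form of CBT.

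These are text edits in three places and need no new data or analysis. The downside is a less device-specific claim, which is as far as the evidence goes.
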